8.4 Chest X-ray and Pregnancy Test

Data for Chest X-ray and Pregnancy Test will be collected whenever there is clinical indication. Clinically significant result of Chest X-ray and positive result of Pregnancy Test will be presented in the following lists.

- *List. Clinically Significant Chest X-ray – Safety Set*
- *List. Positive Pregnancy Test – Safety Set*

8.5 Other Safety Measures

8.5.1 Vital Signs

Vital Sign parameters (Systolic Blood Pressure, Diastolic Blood Pressure, Pulse, Body Temperature, Respiratory Rate, and Weight) and the change from baseline at each scheduled visit will be summarized with descriptive statistics by visit and treatment group.

Data will be summarized in the following table.

- *Table. Vital Signs [Parameter] – Safety Set*

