**Table 3. Noncompartmental Mean Pharmacokinetic Parameters of YN968D1 after Single or Multiple Oral Doses**

PK Parameter	Single Oral Dose			Multiple Oral Dose of 750 mg			
	500 mg (n=8)	750 mg (n=12)	850 mg (n=8)	Day 1 (n=11)	Day 6 (n=11)	Day 28 (n=11)	Day 56 (n=11)
$C_{max}$ ng/mL	1,521	2,379	2,833	2,421	2,553	2,210	1,854
(%CV)	(75.1)	(55.9)	(90.0)	(68.5)	(52.8)	(45.5)	(51.2)
$t_{max}$ hour (range)	3.5 (3.0-8.0)	3.0 (2.0-4.0)	4.0 (1.5-8.0)	3.0 (2.0-8.0)	4.0 (3.0-8.0)	4.0 (2.0-6.0)	3.0 (2.0-6.0)

PK Parameter	Single Oral Dose			Multiple Oral Dose of 750 mg			
	500 mg (n=8)	750 mg (n=12)	850 mg (n=8)	Day 1 (n=11)	Day 6 (n=11)	Day 28 (n=11)	Day 56 (n=11)
AUC 0-24 ng.hr/mL (%CV)	11,295 (68.7)	18,172 (59.3)	21,975 (80.8)	19,399 (60.5)	25,449 (59.2)	19,946 (43.2)	15,629 (63.2)
t 1/2λz hours (%CV)	8.1 (30.7)	9.0 (15.1)	9.1 (33.1)	8.9 (25.8)	11.0 (56.7)	11.3 (66.5)	8.3 (61.0)

Abbreviations: Cmax, maximum plasma concentration; CV, coefficient of variation; tmax, time to reach Cmax; AUC0-24, area under plasma concentration-time curve; t1/2λz, half-life associate with terminal slope of a semilogarithmic concentration-time curve

The safety population comprised all subjects who had received at least 1 dose of YN968D1 (N=46). The most frequently observed adverse drug reactions were hypertension (69.5%, 29 grade 1-2 and 3 grade 3-4), proteinuria (47.8%, 16 grade 1-2 and 6 grade 3-4), and hand-foot syndrome (45.6%, 15 grade 1-2 and 6 grade 3-4). Hypertension was generally manageable with antihypertensive agents. Approximately 10 % of the subjects who developed HFS progressed to Grade 3. Other treatment-related AEs were generally mild or moderate in severity and were manageable. The treatment was discontinued for both of the two subjects who experienced DLT. After recovery, one (1) subject was able to reinitiate treatment at a reduced dose. A total of 15 subjects received at least one cycle of YN968D1 at the initial dose. Four (4) subjects discontinued the treatment during Cycle 1, of which 1 subject in the 250 mg dose group due to disease progression and 3 in the 1,000 mg dose group due to intolerable toxicity. Eighteen (18) subjects had a dose reduction for different toxicities during the extended treatment (1 in 1,000 mg group, 13 in 850 mg group, and 4 in 750 mg group). For those subjects who experienced dose reduction, the mean duration of treatment with YN968D1 was 5.4 months.

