### 4.7. Prior and Concomitant Medications

#### 4.7.1. Contraindicated Treatment

The following treatments or medications are contraindicated during the Treatment period. If any of these treatments/medications is administered, the subject should be withdrawn from the study treatment.

- While patients are on treatment cycle of this study, other anticancer therapy, systemic chemotherapy, radiotherapy (Radiation as a palliative therapy to treat bone metastasis will be allowed.), immunotherapy, cancer-related hormone therapy (cancer unrelated alternative hormone therapy that was initiated prior to the study enrollment is allowed) or herbal medicines that have official indication as anticancer drugs, or administration of investigational products from other

clinical studies are not permitted.

- The use of hematopoietic factors such as G-CSF etc. during the Japan DLT assessment period will be prohibited in the protocol.
- Packed red blood cell transfusion or erythropoietin therapy are not permitted within 14 days prior to the study enrollment (however, permitted if stable condition was maintained by erythropoietin therapy for at least 1 month prior to the enrollment). Packed red blood cell transfusion or erythropoietin therapy can be used after the initiation of the treatment at the investigator's discretion and their use must be recorded in the eCRF. (Erythropoietin therapy is not approved for the anemia associated with cancer chemotherapy in Japan)
- Medications known or suspected to prolong the QT/QTc interval, with the exception of drugs with low risk of QT/QTc prolongation. This includes but not limited to the following drugs;
  - Antibacterial drugs: Clarithromycin, Azithromycin, Erythromycin, Roxithromycin, Metronidazole, Moxifloxacin
  - Antiarrhythmic drugs: Quinidine, Sotalol, Amiodarone, Disopyramide, Procainamide
  - Antipsychotics: Risperidone, Fluphenazine, Droperidol, Haloperidol, Thioridazine, Pimozide, Olanzapine, Clozapine
  - Antifungals: Fluconazole, Ketoconazole
  - Antimalarials: Mefloquine, Chloroquine
  - Antidepressants: Amitriptyline, Imipramine, Clomipramine, Dothiepin, Doxepin
- Strong inducers or inhibitors of CYP3A4, CYP2C9, and CYP2C19. This includes but not limited to the following drugs (refer to <http://www.fda.gov/Drugs/DevelopmentApprovalProcess/DevelopmentResources/DrugInteractionsLabeling/ucm093664.htm>);
  - CYP3A4 inducers or inhibitors: Diltiazem, Itraconazole, Ketoconazole, Posaconazole, Voriconazole, Clarithromycin

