8.5.2 Physical Examination

Subjects with at least once clinically significant abnormal result at all time points after first IP administration on physical examination will be summarized by treatment group. Clinically significant result of physical examination will be listed.

Data will be summarized in the following table and list.

- *Table. Clinically Significant Physical Examination – Safety Set*
- *List. Subjects with Clinically Significant Abnormal on Physical Examination – Safety Set*

8.5.3 12-lead Electrocardiogram

Values for ECG parameters (Heart rate, PR interval, QTcF and RR Interval) and the change from baseline will be summarized with descriptive statistics by time point and treatment group. The ECG result will be presented in shift tables (Normal, Abnormal NCS, or Abnormal CS) from baseline to each scheduled time point by time point and treatment group. Significant shift from baseline will be tested using McNemar's test.

Data will be summarized in the following tables and list.

- *Table. 12-lead Electrocardiogram [Parameter] – Safety Set*
- *Table. Shift from baseline on 12-lead ECG – Safety Set*
- *List. Subjects Shifting from Normal or NCS at baseline to CS at Post-Treatment on 12-lead ECG – Safety Set*

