10.2 Summary Statistics

Summary statistics for continuous variables/endpoints will be presented with number of observations (n), mean, standard deviation (SD), median, minimum (min), and maximum (max). Summary statistics for categorical variables/endpoints will be presented with counts (n) and percents. Unless otherwise specified, denominator of percentage is number of subjects included in the analysis set by each group.

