11.2 Repeated or Unscheduled Assessments

In case there are measurements from an unscheduled visit after the first dose of the investigational product, measurements at scheduled and unscheduled visit are chronologically presented in the subject list whereas summary of descriptive statistic by time point will only include measurements at scheduled visits.

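### Measured blood pressure and QTcF values are summarised only by visit or time point, so no table counts how many subjects had a raised value; add subject-level worst-value tables to SAP 8.5.1 and 8.5.3

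*SAP*

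**What the plan says.** **Blood pressure.** SAP 8.5.1 plans a single table: systolic and diastolic values, and "the change from baseline at each scheduled visit will be summarized with descriptive statistics by visit and treatment group". SAP 10.2 defines the summary as the number of observations plus "mean, standard deviation (SD), median, minimum (min), and maximum (max"). SAP 11.2 restricts it further: "summary of descriptive statistic by time point will only include measurements at scheduled visits". Unscheduled readings go to subject lists only, and SAP 8.5.1 names no vital-sign list.

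**QTcF.** SAP 8.5.3 reads: "Values for ECG parameters (Heart rate, PR interval, QTcF and RR Interval) and the change from baseline will be summarized" by time point and arm. It then adds "The ECG result will be presented in shift tables (Normal, Abnormal NCS, or Abnormal CS"), with a list of subjects who move to clinically significant. That classification is of the ECG result as a whole, not of the QTcF number.

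**Other safety data.** Laboratory results get a shift to worst CTCAE grade (SAP 8.3), physical examination an ever-abnormal table (8.5.2), and ECOG status a shift table (8.5.4). Protocol 8.3.7 allows a normal/abnormal shift summary where necessary, in a section that covers vital signs. The SAP does not take this up for blood pressure, and SAP 13 gives no reason.

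**Why these two variables.** In the phase I results in Protocol 1.2, "The most frequently observed adverse drug reactions were hypertension (69.5%, 29 grade 1-2 and 3 grade 3-4"). Grade 3 or higher hypertension is a listed discontinuation criterion, subject to investigator judgement (Protocol 6.2, item 4). For QTcF, exclusion 16 sets numeric limits at entry, and Protocol 4.7.1 bars "Medications known or suspected to prolong the QT/QTc interval", apart from low-risk drugs.

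**The concern.** The clinical question is how many subjects had a raised reading and how high it went. A by-visit summary answers a different one: where the arm stood on average on a given day. If a rise is brief, or treated before the next fortnightly visit, each affected subject adds to one visit and not to the others, so the visit mean understates the number ever affected. The minimum and maximum in the same table do not repair this, because a visit maximum is one subject's value. A reading taken between visits because of a problem is left out altogether.

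At stake is the report's ability to check hypertension adverse events against measured data. An adverse event entry depends on a site judging the finding clinically significant. The recorded pressures are the independent evidence, and as planned they cannot say how many subjects were affected. The same applies to the upper tail of QTcF.

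**Working it through.** **1. The plan's own figure.** Phase I hypertension: (29 + 3)/46 = 69.57%, printed as 69.5%. Proteinuria was 22/46 = 47.8% and hand-foot syndrome 21/46 = 45.65% (printed 45.6%), so hypertension was the most frequent in phase I. The earlier phase III trial in Protocol 1.2 names it third of three, without rates. Grade 3-4 alone was 3/46 = 6.5%.

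**2. Inputs.** From the documents: about 459 subjects at 2:1, so 306 v 153; visits every two weeks, so four per eight weeks. Assumed: a 30 mmHg rise (range 20 to 40) at one of four visits and back to baseline at the others; SD of change 15 mmHg; all subjects observed. The SAP plans no test on vital signs, so the detection probabilities below only measure how much information each summary keeps.

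**3. Infrequent severe rise.** Mean difference at a visit = excess proportion × rise ÷ 4.
- 3/46 × 30 ÷ 4 = 0.49 mmHg (0.33 at 20 mmHg, 0.65 at 40 mmHg).
- SE = 15 × √(1/306 + 1/153) = 1.49 mmHg.
- Chance of showing it at two-sided 5%: 6.3% (5.6% to 7.2%).
- The same 6.5-point excess as a proportion of subjects, at assumed placebo rates of 2%, 5% and 10%: about 85%, 65% and 47%.

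**4. Common rise of any grade.** 32/46 against an assumed 5% to 20% on placebo, all else as above.
- (0.696 − 0.05) × 30 ÷ 4 = 4.8 mmHg; (0.696 − 0.20) × 30 ÷ 4 = 3.7 mmHg.
- Chance of showing it at a visit: 90% and 71%. Over rises of 20 to 40 mmHg: 2.5 to 6.5 mmHg, and 39% to 99%.
- As a subject count, 69.6% v 10% is detected with probability above 0.999.

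**5. How much control dilutes the mean.** Arm mean change = share affected × rise × (1 − share back to baseline). With 69.6% affected and rises of 15 to 30 mmHg:

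| Share back to baseline at the visit | Mean change (mmHg) |
|---|---|
| none | 10.4 to 20.9 |
| half | 5.2 to 10.4 |
| 75% | 2.6 to 5.2 |
| 90% | 1.0 to 2.1 |

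The mean approaches zero only with about 90% or more back to baseline, or when few subjects are affected.

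**6. A trap in the obvious remedy.** More time on treatment means more readings, and so more chances to cross a threshold. Protocol 1.2 gives median PFS of 2.6 v 1.8 months in the earlier phase III trial. Suppose no drug effect on pressure, exponential exposure with those medians, fortnightly readings, mean systolic 122 mmHg, between-subject SD 10 and within-subject SD 8 to 12 (all assumed except the medians). Then the share ever at or above 140 mmHg is about 18% v 15% (SD 8) to 33% v 28% (SD 12). That is a spurious excess of roughly 3 to 5 points on active drug, which moves by a point or so with details of the simulation.

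A two-cycle window shrinks this without removing it. Day 56 is 56 × 12/365.25 = 1.84 months, when 0.5^(1.84/2.6) = 61% v 0.5^(1.84/1.8) = 49% would still be on treatment.

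**The case against.** The best defence is that hypertension is already counted elsewhere. Protocol 5.3.1 brings clinically significant findings, including those needing unscheduled treatment, into the adverse event assessment. SAP 8.2.2 tabulates subjects by worst CTCAE grade and preferred term in each arm. SAP 8.2.3 tabulates events leading to discontinuation, reduction or interruption. SAP 7.4 compares concomitant drug classes between arms. For ECGs, Protocol 5.3.6 makes clinically significant findings adverse events and asks for tracings to be sent to the sponsor for further evaluation. All of this stands, so a reader who infers that the trial would miss hypertension goes too far.

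A reader might also infer that blood pressure is analysed only as mean change and would average to near zero, so that the vital-sign tables contradict the adverse event rate. The documents do not support that. Values, median, minimum and maximum are shown too. The dose adjustment plan (Protocol 4.4) makes no change for Grade I non-hematological toxicity and withholds only at Grade III or IV, and 29 of the 32 phase I cases were Grade 1-2. That every rise has gone by the next visit is therefore an assumption. A rise as common as in phase I would still show as several mmHg. Nor is QTcF handled just as blood pressure is, since the ECG result has a shift table and a list.

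Finally, 140/90 mmHg and 450/470 msec are entry criteria in the protocol, and exclusion 15 also requires a recent medication change. Neither is an on-treatment outcome definition. That stands, and limits how the figures may be used.

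None of this supplies a subject-level count from the measured values.

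**Conclusion.** The gap is real but bounded. As planned, measured blood pressure has no worst value, threshold count, shift table or named list, and numeric QTcF has no outlier categories, while most other safety data get a shift or ever-abnormal table.

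The loss depends on the pattern. For a severe rise in about 6.5% of subjects at one visit in four, the mean moves by 0.33 to 0.65 mmHg and is in effect invisible; a subject count would show it with probability of about 47% to 85%. For a rise as common as in phase I, the mean still moves by about 2.5 to 6.5 mmHg. Dilution is therefore the supportable word. These sizes rest on assumed rises, SD, placebo rates and recovery. The severe-rise detection figures use the Grade 3-4 rate, not the 140/90 count proposed below.

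The consequence is that the measured data cannot corroborate adverse event reporting at subject level. No primary or key secondary inference is affected. The amendment is worth making because the harm is known and the data are already collected.

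**What to change.** Keep the existing tables and amend the SAP before unblinding.

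- **8.5.1:** add the maximum post-baseline on-treatment systolic and diastolic value per subject, including unscheduled readings. Add a baseline-to-worst table with the number and percentage by arm reaching systolic ≥140 or diastolic ≥90 mmHg among subjects below both at baseline.
- **8.5.3:** add the number and percentage by arm with maximum post-baseline QTcF above 450 msec (males) or 470 msec (females), and the maximum QTcF increase per subject.
- **Status of the figures:** state that they come from the eligibility criteria and serve only as reporting categories, not as clinical rules.
- **Comparison between arms:** give the difference and 95% CI over a common early window (for example scheduled visits in the first two cycles) or adjusted for exposure. Show the whole on-treatment period descriptively, with the number of subjects contributing readings at each visit.

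The cost is SAP wording and two or three more safety tables. Sample size, alpha and data collection do not change. The downside is that the counts must be read alongside exposure, since a window reduces the effect of unequal time on treatment but does not remove it.

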8.5.2 Physical Examination

Subjects with at least once clinically significant abnormal result at all time points after first IP administration on physical examination will be summarized by treatment group. Clinically significant result of physical examination will be listed.

Data will be summarized in the following table and list.

- *Table. Clinically Significant Physical Examination – Safety Set*
- *List. Subjects with Clinically Significant Abnormal on Physical Examination – Safety Set*

8.5.3 12-lead Electrocardiogram

Values for ECG parameters (Heart rate, PR interval, QTcF and RR Interval) and the change from baseline will be summarized with descriptive statistics by time point and treatment group. The ECG result will be presented in shift tables (Normal, Abnormal NCS, or Abnormal CS) from baseline to each scheduled time point by time point and treatment group. Significant shift from baseline will be tested using McNemar's test.

Data will be summarized in the following tables and list.

- *Table. 12-lead Electrocardiogram [Parameter] – Safety Set*
- *Table. Shift from baseline on 12-lead ECG – Safety Set*
- *List. Subjects Shifting from Normal or NCS at baseline to CS at Post-Treatment on 12-lead ECG – Safety Set*

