### 5.3.3. Vital Signs and Physical Findings

Body temperature (oral, axillary, core, temporal, or tympanic), blood pressure (systolic/diastolic), heart rate, and respiratory rate will be collected as vital signs. Vital signs will be measured at every visit with the subject in a sitting position at rest for at least 5 minutes. Systemic physical examination will be performed within 14 days before the date of randomization and at every study visit thereafter.

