#### **Other safety endpoints including laboratory test results and vital signs**

For the analysis of safety data, including laboratory values, vital signs, physical examination, 12-lead ECG and ECOG performance status, continuous variables will be summarized using descriptive statistics (mean, median, SD, minimum and maximum) and categorical variables will be summarized using numbers and percentages of subjects. If it is necessary, a normal/abnormal shift of the safety endpoint will be summarized.

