5.9.9 Physical Examination

Any abnormal physical findings on eye, ears, nose, throat, neck, thyroid, cardiovascular system, respiratory system, gastrointestinal system or mouth, dermatologic system, extremities, musculoskeletal system,

central and peripheral nervous system, lymph nodes will be collected. Whether the finding is clinically significant will also be checked.

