8.3 Clinical Laboratory Evaluation

Laboratory data will be classified according to CTC Grade (NCI-CTCAE version 4.03). A shift table from baseline to worst NCI-CTC grade will be presented.

- *Table. Shift from Baseline of Hematology Tests by Worst NCI-CTC Grade: Rivoceranib + BSC [Parameter] – Safety Set*
- *Table. Shift from Baseline of Hematology Tests by Worst NCI-CTC Grade: Placebo + BSC [Parameter] – Safety Set*
- *Table. Shift from Baseline of Blood Chemistry Tests – serum electrolyte by Worst NCI-CTC Grade: Rivoceranib + BSC [Parameter] – Safety Set*
- *Table. Shift from Baseline of Blood Chemistry Tests – serum electrolyte by Worst NCI-CTC Grade: Placebo + BSC [Parameter] – Safety Set*
- *Table. Shift from Baseline of Blood Chemistry Tests – liver enzymes by Worst NCI-CTC Grade: Rivoceranib + BSC [Parameter] – Safety Set*
- *Table. Shift from Baseline of Blood Chemistry Tests – liver enzymes by Worst NCI-CTC Grade: Placebo + BSC [Parameter] – Safety Set*
- *Table. Shift from Baseline of Blood Chemistry Tests – others by Worst NCI-CTC Grade: Rivoceranib + BSC [Parameter] – Safety Set*
- *Table. Shift from Baseline of Blood Chemistry Tests – others by Worst NCI-CTC Grade: Placebo + BSC [Parameter] – Safety Set*

- *Table. Shift from Baseline of Coagulation Tests by Worst NCI-CTC Grade: Rivoceranib + BSC [Parameter] – Safety Set*
- *Table. Shift from Baseline of Coagulation Tests by Worst NCI-CTC Grade: Placebo + BSC [Parameter] – Safety Set*

To investigate a normal/abnormal shift from baseline by visit, results will be classified as Normal, Abnormal NCS, or Abnormal CS and presented with a shift table. Subjects who were 'Normal' or 'Abnormal - not clinically significant (NCS)' at baseline but shifted to 'Abnormal - clinically significant (CS)' will be summarized in the following tables and listings. Significant shift from baseline will be tested using McNemar's or Bowker's test.

- *Table. Shift from Baseline of Hematology Tests [Parameter] – Safety Set*
- *Table. Shift from Baseline of Blood Chemistry Tests – serum electrolyte [Parameter] – Safety Set*
- *Table. Shift from Baseline of Blood Chemistry Tests – liver enzymes [Parameter] – Safety Set*
- *Table. Shift from Baseline of Blood Chemistry Tests – others [Parameter] – Safety Set*

- *Table. Shift from Baseline of Coagulation Tests [Parameter] – Safety Set*

- *Table. Shift from Baseline of Urinalysis Tests [Parameter] – Safety Set*

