10.5 Baseline

Baseline is defined as the value at Cycle 1 Day 1, or the last value observed prior to randomization if this is not available.

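### The physical-examination table in SAP 8.5.2 ignores baseline, so clinically significant findings already present before dosing are counted together with new ones

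*SAP*

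**What the plan says.** SAP 8.5.2 (Physical Examination) specifies one table and one listing on the Safety Set. The table is to cover "Subjects with at least once clinically significant abnormal result at all time points after first IP administration on physical examination", by treatment group. The listing gives the CS results. Baseline status is not mentioned. The text also does not say whether the table is one pooled row or is split by body system.

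For laboratory tests, SAP 8.3 works differently: "To investigate a normal/abnormal shift from baseline by visit, results will be classified as Normal, Abnormal NCS, or Abnormal CS" in a shift table, and subjects who were normal or abnormal-NCS (not clinically significant) "at baseline but shifted to 'Abnormal - clinically significant (CS)' will be summarized". SAP 8.5.3 and 8.5.4 use shift tables for ECG and ECOG, and SAP 8.5.1 uses change from baseline for vital signs.

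Protocol 8.3.7 names physical examination among the other safety endpoints and leaves a shift summary optional: "If it is necessary, a normal/abnormal shift of the safety endpoint will be summarized". The SAP takes up that option for laboratory, ECG and ECOG data but not for physical examination. It gives no reason, and SAP 13 (Change from Protocol) does not mention the matter.

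**The concern.** The population has advanced or metastatic gastric cancer after at least two prior lines of treatment. Some subjects can be expected to enter with standing CS findings, and physical examination is repeated about every two weeks on treatment, so a standing finding has many chances to be recorded again after the first dose. Under SAP 8.5.2 one such record makes the subject a case.

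The table then mixes two quantities: findings that were already there, and findings that arose or became significant on treatment. A safety reader wants the second. The table is also of some use as a check on adverse event reporting, since it comes from scheduled examinations and does not depend on an event being reported. It serves that purpose poorly if old and new findings cannot be told apart.

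The wording has a second, smaller fault. It joins a condition met by a single result to a phrase about every time point, so a programmer has to guess which applies.

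**Working it through.** The plan states no figure on this point, so there is none to reproduce. The check is a comparison of sections, then a short piece of algebra.

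**1. Is physical examination treated differently?**

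| Safety data | SAP section | Reference to the pre-dose state |
|---|---|---|
| Adverse events | 5.9.2, 8.2 | Yes: starts on or after first dose, or worsens after it |
| Laboratory tests | 8.3 | Yes: shift from baseline, and normal/NCS to CS |
| Vital signs | 8.5.1 | Yes: change from baseline |
| Physical examination | 8.5.2 | None |
| ECG | 8.5.3 | Yes: shift tables; listing of normal/NCS to CS |
| ECOG | 8.5.4 | Yes: shift tables |

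Physical examination is the only row without one.

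**2. Are the data for a baseline comparison collected?** Yes.
- Protocol 5.3.3: "Systemic physical examination will be performed within 14 days before the date of randomization and at every study visit thereafter". Protocol 3.4.2 repeats the examination at Cycle 1 Day 1, and the study schedule (Protocol Table 1) places it before dosing.
- SAP 10.5: "Baseline is defined as the value at Cycle 1 Day 1, or the last value observed prior to randomization if this is not available".
- SAP 5.9.9 collects abnormal findings by body system and adds: "Whether the finding is clinically significant will also be checked".

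**3. What does the missing baseline condition do?** Within one row of the table, let b be the share of subjects with a CS finding at baseline that is recorded as CS again after dosing, equal in both arms. Let p1 and p0 be the risks of a new CS finding on active drug and placebo among the rest.
- Observed risk in an arm = b + (1 − b)p.
- Observed difference = [b + (1 − b)p1] − [b + (1 − b)p0] = (1 − b)(p1 − p0).
- Observed ratio = [b + (1 − b)p1] / [b + (1 − b)p0], which moves toward 1 as b rises.

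The documents give none of b, p1 or p0. As an illustration only, assume p1 = 20% and p0 = 10%:

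| Assumed b | Rule in SAP 8.5.2 | Difference | Ratio |
|---|---|---|---|
| 0% | 20% v 10% | 10 points | 2.0 |
| 20% | 0.2 + 0.8 × 0.20 = 36% v 0.2 + 0.8 × 0.10 = 28% | 8 points | 36/28 = 1.29 |
| 40% | 0.4 + 0.6 × 0.20 = 52% v 0.4 + 0.6 × 0.10 = 46% | 6 points | 52/46 = 1.13 |

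**4. What does counting only new CS findings change?** Against the full Safety Set the rate is (1 − b)p. At b = 20% that is 16% v 8%: the difference is still 8 points, but the ratio is back to 2.0. Against subjects not CS at baseline it is 20% v 10%, which restores both. The two denominators answer different questions, so both are worth showing.

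**The case against.** The strongest reply is that little depends on this table.

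- **Hand-foot syndrome.** A reader might infer that this known drug effect would be diluted or lost. The documents do not support that. Under SAP 5.9.1 clinically significant changes in examination findings are adverse events. SAP 8.2 limits the adverse event tables to treatment-emergent events, displays them by system organ class, preferred term and grade, and repeats them for adverse drug reactions. A summary that takes the pre-dose state into account therefore already exists. This stands.
- **Pooling.** Tumour findings in the abdomen or lymph nodes could mask skin or extremity findings only if all body systems share one row. SAP 5.9.9 collects dermatologic findings and extremities separately, and SAP 8.5.2 does not say that they are pooled. In a table by system, b for the skin rows would not include findings elsewhere. This stands too, although an unchanged finding within a system would still be counted.
- **No test.** A reader might turn the attenuation into lost power. The table is descriptive, no test is planned on it, and every rate above is assumed, so a power figure would describe no planned analysis.
- **Protocol compliance.** Protocol 8.3.7 makes the shift summary optional, so its absence is not a deviation. That is correct; the point is inconsistency within the SAP.
- **The listing.** The listing of CS results is not expressly limited to post-dose visits, so baseline findings may be visible there. That helps a reader of individual records but not a reader of the table.

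None of this answers the gap itself: the table cannot separate old findings from new ones, although the data to do so are collected.

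**Conclusion.** The point holds as a minor inconsistency with a near-free remedy. SAP 8.5.2 counts persisting pre-dose CS findings as if they were new, unlike the SAP's other safety summaries.

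The effect is attenuation of any between-arm contrast in this one descriptive table. In each row the difference shrinks by the factor (1 − b) and the ratio moves toward 1. The size cannot be stated, because the documents give no baseline rate of CS findings. The range shown (ratio 2.0 falling to 1.29 or 1.13) rests on assumed risks, equal carry-over in both arms, and every baseline finding counted in b being recorded as CS again after dosing.

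Randomization should balance carry-over in expectation, so there is no reason to read this as a bias favouring one arm. Nor does it show that hand-foot syndrome or another main harm would be missed, since the treatment-emergent event tables cover those.

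**What to change.** Reword SAP 8.5.2 as follows.

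- Present, by body system and treatment group, a shift table from baseline (not CS, CS) to the worst result after first dose, using the baseline definition in SAP 10.5.
- Show the number of subjects not CS at baseline who became CS after first dose, as a percentage of the Safety Set and of those not CS at baseline in that system. The second denominator must be stated: SAP 10.2 defaults to the full analysis set, and neither SAP 8.3 nor SAP 8.5.3 specifies a restricted one.
- Replace the unclear time condition with: at any time after first IP administration.
- Keep the full listing of CS results.

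A full shift table is preferable to dropping subjects who are CS at baseline. A subject with an existing extremity finding who then develops another there stays visible in the CS-to-CS cell. That cell cannot show that the later finding is different; the listing and the adverse event tables have to do that.

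The cost is one extra table layout and some added programming. No new data are needed, and no visit, dose or clinical rule changes.
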